8.2. Subject Exclusion Criteria

1. Received additional therapy for the treatment of uveitis or prohibited medication as defined in Section 6.2 of the Parent protocol, CLS1001-301
2. Require additional therapy for the treatment of uveitis or prohibited medication as defined in Section 6.2 of the Parent protocol, CLS1001-301 at the time of the Crossover visit

8.3. Subject Withdrawal Criteria

Subjects may withdraw from the study at any time and for any reason without obligation. Subjects may be removed from the study at the Investigator's discretion or if they require Rescue due to disease progression that warrants further treatment.

If a subject withdraws from the study or if the Investigator removes a subject from the study, the Investigator should make every attempt to complete all Visit 4 assessments ([Section 20.1. - Appendix A](#)). If at any time during the study a subject is considered at immediate risk for a vision-threatening event due to study participation, the subject should be treated as soon as necessary, with the investigator determining appropriate care or additional therapy ([Section 9.2.2.](#)).

9. TREATMENT OF SUBJECTS

9.1. Description of Study Drug

No study drug will be administered in the MAGNOLIA study.

9.1.1. Study Eye Determination

The study eye will remain the same as in the Parent study, CLS1001-301.

9.1.2. Treatment of the Fellow Eye (Non-Study Eye)

Ocular therapy for the fellow eye is not subject to the requirements of this protocol. Local medications are permitted for the fellow eye during the course of this trial. Systemic therapy for diseases of the fellow eye is subject to the list of medications below and will be considered additional therapy for the study eye. Medications used in the fellow eye will be recorded in the subject's medical chart and the case report form (CRF).

9.2. Concomitant Medications

9.2.1. Medications for treatment of uveitis

If additional therapy is necessary to treat uveitis in the study eye and normal standard of care requires these medications, they will be recorded in the subject's case report form and should follow the guidelines presented for rescue criteria. The list of medications provided below is not intended to be comprehensive, but rather to help guide the Investigator's medical judgment. If any of these medications are used during the study, the subject will be considered to have received additional therapy for uveitis and should be exited from the study (Section 19.1.).

- Increases in dose of topical ophthalmic NSAIDs in the study eye
- Any corticosteroid implant (ie, Ozurdex[®], Iluvien[®] or Retisert[™]) in the study eye
- Topical, periocular or intravitreal corticosteroids in the study eye
- Increases in dose of systemic prednisone or other equivalent steroid (eg, dexamethasone), including, but not limited to, the following routes: oral, intravenous, intramuscular, in sufficient doses and/or for sufficient time such that the Investigator has concerns about additional ocular exposure to steroids in terms of safety and/or efficacy
- Anti-angiogenic drugs (anti-VEGF) in the study eye or systemically (including pegaptanib sodium, bevacizumab, ranibizumab)
- Increases to dose of systemic immunosuppressant drugs
- Acetazolamide (Diamox[®])
- Any investigational drug or device

In cases where a subject presents with a medication not included on the above list, or should there be any question on the part of the Investigator, Investigators are encouraged to confer with the Medical Monitor for any clarification.

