2. SYNOPSIS

| | |
|--|--|
| Name of Sponsor/Company: Clearside Biomedical, Inc. | |
| Name of Investigational Product: Triamcinolone Acetonide (CLS-TA) Injectable Suspension | |
| Name of Active Ingredient: Triamcinolone Acetonide | |
| Title of Study: MAGNOLIA: Multi-Center, Non-Interventional Extension Study of the Safety and Efficacy of CLS-TA for the Treatment of Macular Edema associated with Non-Infectious Uveitis | |
| Study center(s): Multi-Center | |
| Principal Investigator: Multi-Center | |
| Studied period: 6 Month Duration Estimated date first patient enrolled: October 2016 Estimated date last patient completed: September 2017 | Phase of development: Non-interventional study |
| Objectives: Primary: Demonstrate the maintenance of efficacy of CLS-TA, up to 6 months following exit from Parent study, as shown by the need for additional therapy or the increase in maintenance therapy, for the symptoms of uveitis. Secondary: Determine the maintenance of safety of CLS-TA up to 6 months following exit from Parent study, as demonstrated by incidence of adverse events related to Parent study investigational product | |
| Number of patients (planned): approximately 30 | |
| Diagnosis and main criteria for inclusion: Participation in CLS1001-301, non-infectious uveitis Phase 3 (Parent) study without additional therapy for uveitis | |
| Investigational product, dosage and mode of administration: No investigational product administered in this study | |
| Reference therapy, dosage and mode of administration: None | |
| Criteria for evaluation: Efficacy: Mean time to additional uveitis therapy or change in maintenance therapy for uveitis Safety: Incidence of Adverse Events and serious adverse events grouped by organ system, relatedness to Parent study investigational product, and severity | |
| Statistical methods: All data collected in the study database will be presented in the listings. Listings will include change from baseline. Baseline is the Crossover Visit. Time to Rescue Therapy will be analyzed using Kaplan-Meier analysis including 95% confidence intervals, log rank p-value for difference between treatments, and quartiles. | |

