6.1. Primary Objective

Demonstrate the maintenance of efficacy of CLS-TA, up to 6 months following exit from Parent study, as shown by the need for additional therapy or the increase in maintenance therapy, for the symptoms of uveitis.

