13.5. Analysis Methods

13.5.1. Primary Efficacy Endpoint

Time to rescue therapy (dosing with a drug when efficacy of the Parent study investigational products is no longer adequate)

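### The primary event is described differently in the synopsis, 6.1, 9.2.1 and 13.5.1, so the same systemic steroid increase for uveitis can be counted as an event or not

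*Combined protocol and SAP*

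**What the plan says.** Four places describe what ends maintained efficacy.

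- Section 6.1 (primary objective): maintenance of efficacy "as shown by the need for additional therapy or the increase in maintenance therapy, for the symptoms of uveitis".
- Synopsis, efficacy criterion: "Mean time to additional uveitis therapy or change in maintenance therapy for uveitis".
- Section 13.5.1 (primary endpoint): "Time to rescue therapy (dosing with a drug when efficacy of the Parent study investigational products is no longer adequate". This is the event that 13.5.2 analyses by Kaplan-Meier and log-rank.
- Section 9.2.1 lists medications with a stated consequence: if one is used, "the subject will be considered to have received additional therapy for uveitis and should be exited from the study". For systemic prednisone or an equivalent steroid, the listed item is a dose increase given "in sufficient doses and/or for sufficient time such that the Investigator has concerns about additional ocular exposure to steroids in terms of safety and/or efficacy". The parallel item for another systemic class reads only "Increases to dose of systemic immunosuppressant drugs", and the topical NSAID item also counts a dose increase without any further condition.

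Two other statements bear on how the list is read. Section 9.2.1 says that it "is not intended to be comprehensive, but rather to help guide the Investigator's medical judgment". Section 9.1.2 says: "Systemic therapy for diseases of the fellow eye is subject to the list of medications below and will be considered additional therapy for the study" (that is, the study eye).

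**The concern.** Raising maintenance prednisone is a natural response when uveitis begins to return. Under 6.1 that increase is evidence that efficacy was not maintained. Under the 9.2.1 item, the same increase makes the subject an additional-therapy case only if the investigator has a particular concern about it, and no dose or duration is given to anchor that concern. The endpoint in 13.5.1 does not say which reading governs.

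If the increase is not counted, the subject stays in the risk set as rescue-free while taking more of the drug class that CLS-TA belongs to. Time to rescue is then too long for that subject. Later BCVA, CST and IOP readings also reflect the added steroid, and the IOP safety endpoints in 13.5.3 use those readings. With about 30 subjects spread over about 40 centers (13.2), the decision would be taken by many investigators with very few subjects each, and without a common rule.

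**Working it through.** The plan gives no figure to reproduce. Section 13.2 bases the sample size on clinical considerations, and no event rate, effect size or arm split is stated. The check is therefore a comparison of sections, followed by simple arithmetic on size.

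**Step 1: one case under each section.** Take a subject whose systemic prednisone is raised for uveitis, where the investigator has no concern about ocular steroid exposure.

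| Section | Is it an event? |
|---|---|
| 6.1 | Yes: maintenance therapy was increased for uveitis |
| Synopsis | Yes: maintenance therapy changed (the word used is not even limited to increases) |
| 9.2.1, steroid item | Not by that item: its condition is not met |
| 9.2.1, list as a whole | Open: the list is guidance and not exhaustive |
| 9.2.2 with 13.5.1 | Yes, if the investigator judges that the study eye has worsened and the drug was given because Parent efficacy had become inadequate; otherwise unclear |
| 9.1.2 (increase given for the fellow eye) | Said to count, but subject to the 9.2.1 list, so the same condition may apply |

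The sections do not agree, and none is given precedence.

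**Step 2: size for the rescue-free proportion.** If one subject's event is never counted, the crude 24-week rescue-free proportion rises by 100/n points.

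- All subjects, n = 30 (7.2 and 13.2): 100/30 = 3.3 points.
- Within an arm (split not stated, so a range is assumed): n = 20 gives 5.0, n = 15 gives 6.7, n = 10 gives 10.0 points.

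A subject who is rescued later contributes a delayed event rather than a missing one, so the effect on the curve is then smaller than these figures.

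**Step 3: direction for the comparison of arms.** The inputs are assumptions, used only to show direction: 24-week event proportions of 30% (CLS-TA) and 60% (sham), proportional hazards, and HR = ln(S_CLS)/ln(S_sham).

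- All events counted: ln 0.70 / ln 0.40 = 0.357/0.916 = 0.39.
- 10 points of events missed in both arms: ln 0.80 / ln 0.50 = 0.223/0.693 = 0.32.
- 20 points missed in both arms: ln 0.90 / ln 0.60 = 0.105/0.511 = 0.21.
- 20 points missed in sham only: ln 0.70 / ln 0.60 = 0.357/0.511 = 0.70.

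Uncounted events always flatter the rescue-free proportion. They can move the treatment comparison either way.

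**The case against.** The strongest reply is that the 9.2.1 list does not define the endpoint. Section 13.5.1 stands on its own, does not refer to the list, and fits a prednisone increase given because the study eye is relapsing. Section 9.2.1 itself opens by sending therapy needed for study-eye uveitis to the rescue criteria. Section 9.2.2 leaves the choice of rescue drug to the investigator and includes worsening by clinical judgement, and 9.3 exits anyone given additional therapy. On this view the qualified steroid item may serve to screen steroid courses given for other diseases, since it names no indication. Section 13 also promises a detailed SAP with data handling conventions.

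Much of this stands. A reader might infer that a prednisone increase for uveitis is excluded from the event unless the investigator has concerns. The documents do not support that, because such an increase can still be classed as rescue. A reader might also infer that the condition concerns drug exposure alone; its closing words cover efficacy as well as safety. And 6.1 does not reach every steroid increase, only one for the symptoms of uveitis. Section 9.1.2 is not an independent unconditional rule either, since it works through the same list.

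What the reply does not do is settle the classification. The 9.2.2 route also rests on individual judgement, 13.5.1 is silent on maintenance increases although 6.1 and the synopsis name them, and the text available contains no event-derivation rule or sensitivity analysis.

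**Conclusion.** The primary event is not defined consistently. A systemic corticosteroid increase given for uveitis is an event under 6.1 and the synopsis, may fall outside the 9.2.1 item, and may or may not be captured by 9.2.2 and 13.5.1. Each such increase that is never counted makes maintenance look better by 3.3 points of the crude rescue-free proportion at n = 30. The total effect cannot be stated, because the documents do not give the number of such increases.

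A reader might go further and infer that the ambiguity favors one arm. The documents do not show that. Sections 7.1 and 9.4 keep the masking until the Parent study is unmasked, and the hazard ratios above rest wholly on assumed rates. The supported conclusion is an ambiguity in the event definition whose known direction is toward overstating maintained efficacy.

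**What to change.** In 13.5.1, define the primary event to match 6.1. The date of an increase in systemic corticosteroid given for uveitis should count as an event whether or not the investigator-concern condition in 9.2.1 is met. Repeat the Kaplan-Meier analysis with that condition applied, as a sensitivity analysis, so that the reader sees how much depends on it. Limiting the rule to increases given for uveitis keeps steroid courses for unrelated disease out of the event.

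The sponsor should also reconcile the synopsis, 6.1, 9.1.2, 9.2.1, 9.2.2 and 13.5.1, including how an increase given for the fellow eye is counted. Which dose change requires exit or treatment is for the sponsor to settle; the change asked for here is to the analysis definition only.

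The cost is some wording and one extra Kaplan-Meier run. Medications are reviewed at every visit (Appendix A), but 13.5.4.6 speaks of additions and deletions, so the sponsor should confirm that the CRF captures the date of and reason for a dose change. The downside is that some minor increases will count as events, so the rescue-free figure may be slightly less favorable.

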9.2.2. Additional Treatment

If at any time during the study a subject is considered at immediate risk for a vision-threatening event, the Investigator should immediately follow best medical practice in the Investigator's judgment for treating the subject. All additional therapy will be recorded in the subject's medical chart and the CRF.

Rescue Criteria

If at any time during the study any of the following criteria are met in the study eye, the use of a treatment should be introduced. The therapy implemented is left to the discretion of the Investigator.

- A loss of 10 or more ETDRS BCVA letters due to uveitis from either of the previous two visits
- CSF > 320 μ m OR an increase in CST of \geq 100 microns or 20%, whichever is lower, from either of the previous two visits
- In the investigator's medical judgement, the uveitic complications in the study eye have worsened and the condition needs to be addressed

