5.2 Scientific Rationale

All subjects entering this trial will have received either CLS-TA or sham procedure from the Parent study, CLS1001-301, as masked investigational product. The objective of the Parent study is to evaluate the safety and efficacy of suprachoroidally administered CLS-TA for the treatment of macular edema associated with non-infectious uveitis. Two doses of CLS-TA or a sham procedure will be performed in the Parent study on each subject enrolled at Day 0 and Month 3 visits and the primary endpoint will be evaluated 6 months following the enrollment.

In addition to providing a robust efficacy and improved safety profile over currently used corticosteroid delivery methods, suprachoroidal administration of precisely delivered local corticosteroid therapy may provide a longer cessation of uveitis symptoms and reduced steroid sensitivity. This potential benefit will be evaluated in this extension study of non-infectious uveitis patients who participated in the Parent study and who have not received additional therapy for uveitis.

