7.2. Number of Subjects

The study population will include approximately 30 adult subjects that successfully complete the Parent study without requiring additional therapy to treat symptoms for uveitis as defined by the protocol. The expected duration of participation in the study is up to 24 weeks from study entry. The complete inclusion and exclusion criteria are presented below in Section 8.

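### Could an eye already above 320 microns at Crossover enter the extension and be counted as an early rescue event?

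*Combined protocol and SAP*

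**What the plan says.** Section 9.2.2 sets the rescue rule: at any time in the study, if "any of the following criteria are met in the study eye, the use of a treatment should be introduced". There are three criteria:

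- a loss of 10 or more letters due to uveitis;
- a thickness criterion with two limbs joined by OR: a level above 320 microns, or a rise of at least the smaller of 100 microns and 20% from either of the previous two visits;
- a judgement by the investigator that "the uveitic complications in the study eye have worsened and the condition needs to be addressed".

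On eligibility, exclusion 2 in Section 8.2 removes subjects who, at the Crossover visit, "Require additional therapy for the treatment of uveitis or prohibited medication as defined in Section 6.2 of the Parent protocol". Section 7.2 describes the population as Parent completers "without requiring additional therapy to treat symptoms for uveitis as defined by the protocol". Section 5.2 describes it as patients "who participated in the Parent study and who have not received additional therapy for uveitis".

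On what rescue means, Section 8.3 allows subjects to be removed "if they require Rescue due to disease progression that warrants further treatment". Section 13.5.1 defines the primary event as dosing once the effect of the Parent study product is insufficient. Section 6.1 judges maintenance of efficacy "as shown by the need for additional therapy or the increase in maintenance therapy", and the Synopsis gives the efficacy criterion as "Mean time to additional uveitis therapy or change in maintenance therapy for uveitis".

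**The concern.** The level limb stands apart from the other criteria. Loss of letters, a rise in thickness and the investigator's judgement all need the eye to get worse; a reading above 320 microns does not. Sections 8.3 and 13.5.1, by contrast, speak of progression or of an effect that has run out.

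The eligibility text does not visibly close the gap. No inclusion or exclusion criterion sets a thickness limit or cites Section 9.2.2. Exclusion 2 points to a section of the Parent protocol that is not supplied, and Section 7.2 does not say which protocol it means. Section 5.2 turns on therapy received, not on therapy needed.

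Suppose, then, that an eye enters at 330 microns, stable or improving. The next scheduled scan is at Week 6. If the level rule is applied then, the subject is treated, exits under Section 9.3 and becomes a primary event. That event would reflect oedema present at entry, not the end of a treatment effect. With about 30 subjects, a few such events would visibly pull down the early part of the curve. With about 40 centers, sites might also read exclusion 2 differently.

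**Working it through.** The plan gives no figure to reproduce: Section 13.2 rests the sample size on clinical considerations and states no event count, effect size or power. The check is therefore a reading of the text, followed by the size per eye.

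**Does the level limb work alone?** Yes. The rise needed on the change limb is min(100, 0.20 × reference). For a reference of 321 microns this is 0.20 × 321 = 64.2, so the eye would have to reach about 385 microns. The level limb is met at 321 with no rise at all. It is the first limb to be reached for any reference above 320/1.2 = 266.7 microns.

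**Can such an eye enter if the protocol is followed?**

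1. Section 9.2.2 applies at any time during the study.
2. Section 7.1 makes the crossover day (Day 0) Visit 1 of the extension and sets eligibility then.
3. Section 11.2 and Appendix A (Section 20.1) require SD-OCT at that visit.
4. Section 9.2.1 says that additional therapy for uveitis should follow the rescue criteria, which links the two terms.
5. Exclusion 2 removes anyone who needs additional therapy at Crossover.

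An eye above 320 microns at Day 0 therefore meets a criterion calling for treatment on the day when needing treatment excludes it. To become an event at Week 6, it must be judged not to need therapy at Day 0 and then be treated for the same level six weeks later.

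**How much would one such eye matter?** Inputs: n = 30 (Section 7.2), next scan at Week 6 and end at Week 24 (Section 7.1). Assumptions: no earlier censoring, and k eyes dosed at Week 6 that would otherwise have stayed event-free.

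- Pooled Kaplan-Meier estimate at Week 6 = 1 − k/30.
- Pooled 24-week restricted mean = 6 + 18 × (1 − k/30).

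| k (assumed) | Kaplan-Meier at Week 6 | Restricted mean (weeks) | Loss (weeks) |
|---|---|---|---|
| 0 | 1.000 | 24.0 | 0 |
| 1 | 0.967 | 23.4 | 0.6 |
| 3 | 0.900 | 22.2 | 1.8 |

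The loss per eye, 18/30 = 0.6 weeks, is an upper bound, because an eye that would have been rescued later anyway loses less.

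A harsher illustration treats the k eyes as rescued at the start and assumes a constant rate giving 40% rescue by Week 24 in the others. The 24-week rescue-free share is then (1 − k/30) × 0.60: 0.60, 0.58 and 0.54 for k = 0, 1 and 3. The first quartile falls at Week 13.5, 11.9 and 8.6.

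These figures describe any early event in a sample of 30. They do not show that this kind of event occurs.

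**The case for a change.** The strongest reply is that the safeguard is inferred. Exclusion 2 does not cite Section 9.2.2, the Parent section it does cite is not available, and an investigator could hold that a stable eye at 330 microns does not need therapy. The sections also describe rescue differently. With few subjects spread over many centers, one sentence of clarification would cost little, and a sensitivity analysis could leave out eyes above the level at Day 0.

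The textual part of this stands: the link is not spelled out, and the descriptions of rescue differ. The rest carries less weight:

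- Sections 5.2 and 7.2 summarise the population. The operative criteria in Section 8.2 cover both therapy received and therapy needed.
- Section 8.3 is a permissive withdrawal clause and does not define the endpoint. Section 6.1 measures maintenance by the need for therapy, so persistent oedema that is treated may be meant to count. Section 13.5.1 leans the other way.
- The trigger for a rescue can largely be worked out from acuity and SD-OCT data taken at every visit. Additional therapy goes in the CRF (Section 9.2.2), and Section 13.5.2 lists all data with change from the Crossover baseline.
- The proposed sensitivity analysis has a cost of its own. Day 0 thickness is measured after Parent treatment, so selecting on it may remove part of a true effect. The extension population is already selected on having avoided additional therapy, and this would be a second such cut in a small sample.

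**Conclusion.** No change to the plan follows. The level limb does trigger rescue without worsening, and the eligibility text does not name it. Followed as written, though, the rescue rule, the Day 0 scan and exclusion 2 most naturally keep such an eye out. What remains is a gap that sites and analysts can fill sensibly, together with a clerical slip: the rescue criterion uses CSF for the level and CST for the change, and only CST is in the abbreviation list.

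If an eye did slip through, it would cost 3.3 percentage points on the pooled curve at Week 6 and at most 0.6 weeks of restricted mean time, given 30 subjects and no earlier censoring. The restricted mean is only a yardstick here, since Section 13.5.2 plans Kaplan-Meier estimates, quartiles and a log-rank test. The number of such eyes is unknown and may be zero. Neither the size nor the direction of a log-rank effect can be determined, because arm sizes and the arms of such eyes are not given.

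The conclusion assumes that investigators apply the same rule at Day 0 and at Week 6, and that the unseen Parent section does not say otherwise. Reconciling the wording of Sections 7.2, 8.2, 8.3, 9.2.2 and 13.5.1 is a matter for the sponsor's clinicians. No view is taken here on which clinical rule should stand, and the planned analysis is the same either way.
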